5.3 Treatment schedule and dose

The treatment regimens for each study group are summarized below (see also Schema above):

- **Group A:** one course of IC, followed by surgical resection, followed by two courses of IC
- **Group B:** surgical resection, followed by three courses of IC

Guidelines for initiation of therapy, following the surgical resection (Course 1 for subjects randomized to Group B and Course 2 for subjects randomized Group A) are provided in Section 5.2. Treatment Courses 1-3 (for Group B) and Courses 2-3 (for Group A) will be repeated every 28 days (+/- 7 days to allow for scheduling constraints) at the same dose, provided that there is no dose limiting toxicity (see Section 5.4) or non-DLT toxicity the treating physician feels warrants dose reduction. Subjects can receive a maximum of 3 courses of therapy. Hu14.18-IL2 will be given on days 1, 2, and 3 of each course of therapy as a 4-hour continuous IV infusion at a daily dose of 6 mg/m²/d. (Note: given the relatively short supply of hu14.18-IL2 available, before each subject begins study treatment, we will confirm with the hospital pharmacy that there is sufficient material available in our pharmacy for that subject to receive all planned doses.) The infusions will be stopped only under the following circumstances: if dose-limiting toxicity is noted (see Section 5.4.4), if the treating physician deems it in the subject’s best interest to discontinue the infusion for a significant, but non-DLT toxicity, when blood draws are needed, when other intravenous medications must be administered, if adequate intravenous access is lost (and a new IV must be placed), and/or if a subject decides to withdraw from the study.

5.3.1 Subsequent Courses:

5.3.1.1 Subjects may continue treatment if all toxicities have recovered to \leq Grade 1 or the subject meets initial eligibility criteria, and there is no symptomatic disease progression (Section 6.0)

5.3.1.2 Course 3 will be administered only to subjects with a documented complete clinical response (i.e., no radiological or clinical evidence of disease) following Course 2 of treatment (see details regarding statistical evaluation in Section 9.5) provided that all toxicity has resolved to \leq Grade 1 or meets initial eligibility criteria.

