5.3.1.3 Subjects not showing CR following surgical resection and 2 courses of study therapy (i.e., at the evaluation following Course 2) will be considered to have progressive disease and will not be eligible for subsequent treatment. In addition, their position in the study group will be filled with a new, randomly assigned subject (see Section 9.3.2 for details). There is always the possibility that clinical or radiographic criteria indicating potential residual melanoma at this time could actually reflect post-operative changes in x-rays or scans or clinical exams, and may not necessarily reflect true progressive/residual disease. Thus, any subject that does not appear to be in CR at this time should have any site of potential recurrent, residual or progressive disease biopsied if that site is considered safely amenable to biopsy (see Section 6.0). In the interest of safety, the biopsy will be performed at least 7 days following the completion of hu14.18-IL2 and as soon after the suspect radiographic data were obtained and/or physical findings were identified (i.e., preferably within 14 days, with efforts not to exceed 21 days). If this biopsy is not consistent with melanoma, the subject may continue with Course 3 of study treatment. Treatment may be delayed to allow for recovery from the biopsy procedure (i.e., preferably no more than a 1-week delay but absolutely not longer than 3 weeks). Decisions related to the duration of time needed to recover from the biopsy, prior to resuming treatment, will be left to the discretion of the treating physician(s). To aid in this decision, laboratory tests may be ordered as warranted clinically, but no specific tests or evaluations are required for this assessment.

In the event that the area of questionable residual disease is not considered safely amenable to biopsy (for example, a small pulmonary nodule that may reflect old infection, atelectasis, or post operative scarring), and is considered potentially to reflect non-malignant post-operative change, the subject may continue with protocol treatment, and will be considered an evaluable subject for this study.

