5.5.1 Criteria for removal from protocol therapy

- a) Progressive disease. Subjects with symptomatic disease recurrence confirmed clinically or radiologically at any time will be removed from protocol therapy. Subjects showing asymptomatic disease recurrence at any of the scheduled clinical monitoring times will be removed from protocol therapy. See Section 6.0 for criteria for recurrent disease.
- b) Drug intolerance (i.e., subjects who experience DLT) at 25% of the starting dose.
- c) Treatment-related toxicities that have not recovered to \leq Grade 2 in 2 weeks following day 3 of any treatment course of hu14.18-IL2.
- d) Refusal of further protocol therapy by subject.
- e) Completion of the 3 allowable courses of therapy.
- f) Physician determines that removal from protocol therapy is in subject's best interest.

Subjects who are off protocol therapy are to be followed until they meet the criteria for Off Study (see Section 5.5.2). Follow-up data will be required unless consent was withdrawn.

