9.2 Definition of Study Endpoints

9.2.1 Primary Endpoints

Pathology evaluations of necrosis, apoptosis, and cellular infiltrate:

Pathology evaluations of necrosis, apoptosis, and cellular infiltrate will be performed on a standard scale with 4 categories: "0" (none), "+" (low), "++" (medium), or "+++" (high). These evaluations will be performed independently by two pathologists in a blinded fashion. In the case of a disagreement, the tumor tissues will be evaluated by a third pathologist.

Time to recurrence (duration of remission):

For a given subject, time to recurrence will be defined as the number of days from the day of evaluation following course 2 of IC treatment to the day the subject experiences an event of recurrence or death, whichever comes first. All subjects on this study have disease deemed to be completely resectable, and all subjects are expected to be going into complete remission following surgical resection. Uniformity of follow up time is best provided by clarifying the time after “study evaluability” that recurrence is first identified (and confirmed whenever possible). As such, the time point of “study evaluability” will be designated the day of evaluation following course 2 of IC treatment, when CR is first demonstrated clinically and radiologically. Subjects in Group A and Group B will each have spent equivalent time since study entry in getting to this point: each will have had their surgical resection and their first 2 courses of IC treatment. The only difference is that surgery is before course 1 for Group A and after it for Group B.

If a subject has not experienced an event of recurrence (or death) at the time of analysis, then the subject’s data will be censored at the date of the last available evaluation

Overall survival:

Overall survival will be defined as the number of days from the randomization to the date of the subject’s death. If a subject is alive at the time of analysis, then the subject’s data will be censored at the date of the last available evaluation

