6	0.38	0.21	0.58
8	0.50	0.31	0.69
10	0.62	0.42	0.79
12	0.75	0.55	0.88
14	0.88	0.68	0.96

Therefore, with a sample size of 16 subjects, the 90% confidence interval for the two-year survival/two-year recurrent-free survival rate will be no wider than 38%.

Secondary endpoints of this pilot study include adverse events, immunological parameters, density & phenotype of cellular infiltrate and expression of GD2 target antigen, and IFN- γ expression. Assuming a total sample size of 16, the probability of observing at least one incidence of Grade ≥ 3 toxicity is 81%, if the true toxicity rate is 10%. Analogously, the probability of observing at least one incidence of Grade ≥ 3 toxicity is 93%, if the true toxicity rate is 15%. Immunological parameters will be measured on a continuous scale. Assuming a sample size of eight subjects per

study arm, a difference of 1.5 standard deviation units in magnitude will be detected with 80% power at a two-sided significance level of 0.05 (based on a two-sample t-test). A difference of only 1.25 standard deviation units will be detected with 63%. Smaller differences are unlikely to be detected as statistically significant.

In order to account for “unevaluable” subjects and drop-outs (e.g., patients without an evaluation following course 2 of IC treatment), we will accrue up to 20 eligible subjects (10 per arm) in total. Based on our past experience with advance melanoma subjects treated at UWCCC, we expect to accrue 20 eligible subjects within 24 months. The minimum follow-up period will be 12 months after the last subject has entered the study.

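### The plan gives no rule for counting subjects who fail or recur before the post-course-2 evaluation, so time to recurrence is most naturally read as a landmark estimate conditional on CR; the OS start dates also conflict

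*Combined protocol and SAP*

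**What the plan says.** **Clock.** Section 9.2.1: "time to recurrence will be defined as the number of days from the day of evaluation following course 2 of IC treatment", ending at recurrence or death. Sections 9.2.1 and 6.4 both identify that evaluation as the one at which CR is first demonstrated.

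**Replacement.** Under Section 5.3.1.3, subjects not in CR after surgery and two courses "will be considered to have progressive disease and will not be eligible for subsequent treatment", and "their position in the study group will be filled with a new, randomly assigned subject". There are two exceptions. A subject whose suspicious site is biopsied and is not melanoma may go on to course 3. If a site cannot safely be biopsied and "is considered potentially to reflect non-malignant post-operative change, the subject may continue with protocol treatment, and will be considered an evaluable subject".

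**Earlier recurrence.** Section 5.5.1(a): "Subjects with symptomatic disease recurrence confirmed clinically or radiologically at any time will be removed from protocol therapy". Section 9.3.2 gives "patients without an evaluation following course 2 of IC treatment" as its example of unevaluable subjects and drop-outs, and covers them by over-accrual: "we will accrue up to 20 eligible subjects (10 per arm) in total".

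**Counting rule.** Section 5.3.1.3 refers to 9.3.2 for details, but 9.3.2 has no such rule. Section 5.3.1.2 says "see details regarding statistical evaluation in Section 9.5", but Section 9 ends at 9.4.9. Section 5.1 sets the target at 16 subjects with surgery and two courses, and Table 9 uses 16 as its denominator.

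**Overall survival.** The start is randomisation in 9.2.1, study evaluability in 6.5, and completion of course 2 in 1.5.4.4.

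**Historical controls.** Section 9.3.2 points to Section 1.3.3, which covers in vitro function of the agent. Section 9.4.4 cites references 47 and 49-53, which by title are integrin papers. The resection outcome data are in Section 1.5.3.

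**The concern.** Time to recurrence belongs to the second primary objective (Section 2.1.2). A subject who is not in CR after course 2 has met the protocol's own definition of progression, yet has no date on which CR was first shown and gives up the place to a new subject. A subject removed earlier for symptomatic recurrence may never have the evaluation at all. If neither is counted, the reported median and two-year rate describe only those who came through the first months successfully, and the reader cannot see how many did not.

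That result is then set beside series whose clock starts at resection and which include early recurrences. Two analysts following this text could also use different denominators for the same data.

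The OS conflict has a similar effect. Under Section 6.5, a subject who never reaches evaluability has no start date; under 9.2.1 every randomised subject has one.

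**Working it through.** **1. Reproduce Table 9.** Wilson score interval, two-sided 90%, z = 1.645, n = 16: centre = (p + z²/2n)/(1 + z²/n); half-width = z·√(p(1−p)/n + z²/4n²)/(1 + z²/n). For 8/16: centre 0.500, half-width 0.190, interval 0.310-0.690. All seven rows agree with the table to two decimals. The widest interval is 0.380, matching the stated 38%.

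**2. Add k uncounted failures on the landmark clock.** The plan does not give k. The cap of 20 less the 16 analysed leaves at most 4.

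| k | Rate | Wilson 90% CI |
|---|---|---|
| 0 | 8/16 = 50.0% | 31.0-69.0% |
| 1 | 8/17 = 47.1% | 29.0-66.0% |
| 2 | 8/18 = 44.4% | 27.2-63.1% |
| 3 | 8/19 = 42.1% | 25.6-60.5% |
| 4 | 8/20 = 40.0% | 24.2-58.1% |

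The last row is an upper bound, because the spare places must also cover subjects who are not resected, do not receive two courses, or drop out for other reasons.

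**3. Time from surgery to the evaluation** (Sections 5.2.1, 5.2.2, 5.3; Table 5, footnotes 1 and 4). Recovery takes 14-28 days. The evaluation falls 7-35 days after day 1 of course 2 (day 8 to day 29 + 7).
- Surgery after course 1: 14-28 + 7-35 = 21-63 days.
- Surgery first: 14-28 + 28-35 (course interval) + 7-35 = 49-98 days.

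**4. How many might fail in that window.** This assumes exponential recurrence and 10 subjects per arm. Expected failures = 10 × Σ(1 − 2^(−w/median)), where the sum is over the two arms and w is the window in months of 30.44 days. The 8-month median is that of one stage IV series in Section 1.5.3. The other two are assumptions, because recurrent stage III is also enrolled.

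| Median | Shortest windows | Longest windows |
|---|---|---|
| 8 months | 1.9 of 20 | 4.1 of 20 |
| 16 months | 1.0 | 2.2 |
| 24 months | 0.7 | 1.5 |

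These counts cannot be paired freely with step 2. Under an exponential, a two-year rate of 50% means a 24-month median, so at most 1.47/20 = 7.4% fail early and the shift is 0.50 × 0.074 = 3.7 points. About four failures arise only with the 8-month median and the longest windows. The two-year rate is then 2^(−24/8) = 12.5%, and 2/16 to 2/20 is a shift of 2.5 points.

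**5. Landmark against a from-surgery analysis.** Starting at surgery restores the early failures but also reads two-year status earlier. The landmark rate is S(w + 24)/S(w); the from-surgery rate is S(24).
- Constant hazard: S(w + 24)/S(w) = S(24), so the net difference is zero.
- Falling hazard, assumed Weibull with shape 0.7 and median 8 months, S(t) = exp(−ln 2 × (t/8)^0.7): S(24) = 22.4%. The landmark rate is 24.6% at w = 21 days and 28.2% at w = 98 days, so it is higher by 2.2 to 5.8 points.

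The documents do not give the shape of the hazard.

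**6. OS start dates.** Take randomisation as the day of the first protocol procedure. With surgery after course 1, surgery falls by day 17 (16 days after day 1), so course 2 starts 28 to 16 + 28 = 44 days after day 1 of course 1. Evaluability follows at 35-79 days. With surgery first it is 49-98 days. The origins in 9.2.1 and 6.5 therefore differ by about 35-98 days (5-14 weeks), plus any wait between randomisation and the first procedure.

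**The case against.** The strongest reply is that exclusion is inferred, not stated. Read alone, the first sentence of the 9.2.1 definition could give a non-CR subject an event at day 0. Section 5.1 describes evaluable subjects by surgery and two courses, without mentioning CR, and Section 1.5.4.4 says all subjects will be followed for time to recurrence. This stands: the documents support a missing counting rule, not a stated exclusion. It does not remove the point, because these readings give different denominators.

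A reader might infer that the plan inflates recurrence-free survival by 10 points, or by 4-15 points at a 75% rate (12/16 to 12/17-12/20). The documents do not support that. Those shifts hold the landmark clock fixed and assume a number of failures the plan does not give; under a constant hazard, such high two-year rates do not go with that many early failures. Nor do the shifts measure the effect of moving to a from-surgery analysis, which is zero under a constant hazard.

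The landmark is also a disclosed choice, made for uniform follow-up when surgery timing differs by arm. It can stay if labelled as such.

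Finally, the historical comparison is qualitative, with no threshold, and Section 9.4.4 also allows other comparable published data. That limits severity. The reference-number errors alone are clerical.

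**Conclusion.** The concern holds as an omission with a likely consequence. Followed in their most natural sense, the replacement rule and the clock give a two-year rate and median conditional on being in CR after course 2, and these are not comparable as they stand with the from-resection data in Section 1.5.3. An all-subject landmark count would be lower by up to 10 points at 8/16; that bound rests on all four spare places going to early failures. Against a from-surgery analysis, the landmark rate is favoured only if the hazard falls with time, by an amount the documents cannot fix.

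The OS contradiction between 9.2.1 and 6.5 is definite. Section 1.5.4.4 names nearly the same point as 6.5, so in practice there are two origins. Since the Overview calls Section 9 the complete analysis plan, the 9.2.1 definition should govern.

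This should be fixed, but severity is modest: no test, error rate or decision threshold depends on it, and the 90% intervals are up to 38 points wide.

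**What to change.** 1. State in 9.2.1 and 9.4.4 that replaced subjects and those who recur before the post-course-2 evaluation stay in the analysis. Add recurrence-free survival with one pre-specified origin: randomisation in all randomised subjects, or surgery in all resected subjects to match the historical series. Count recurrence, failure to show CR after course 2 (with the 5.3.1.3 exceptions), or death as events on the date found. Microscopically positive margins alone are not an event, in keeping with 5.2.3 and 5.5. Keep the post-course-2 analysis as a labelled landmark analysis. Report the number of, and reasons for, replaced and never-resected subjects by arm, naming arms by timing of surgery because Section 9 reverses the Group A and B labels.
2. Analyse OS from randomisation in all randomised subjects, and align 6.5 and 1.5.4.4 with 9.2.1.
3. Editorial: point 9.3.2 and 9.4.4 to Section 1.5.3. Correct the reference numbers there: by title, 82-93 are not melanoma resection series, while melanoma surgery papers are at 76-78, 81 and 95-96. Replace the pointer to Section 9.5.

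The cost is wording and a little more analysis. Follow-up of off-therapy subjects (5.5.1) and survival data after recurrence (6.6) are already planned. Reported rates may become somewhat less favourable.

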9.2.2 Secondary Endpoints

Adverse events:

Adverse events and toxicities (associated with 4 course of IC treatment for 3 consecutive days administered on an every 4-week basis) observed will be categorized according to version 3.0 of the NCI Common Toxicity Criteria.

Biological endpoints:

Biological endpoints include immunological parameters (lymphocyte counts, NK/ADCC, soluble IL2, anti-idiotypic antibodies, and anti Fc-IL2), expression of the GD2 target antigen, density and phenotype of the cellular infiltrate, vascularity, IC binding, IFN- γ expression and T cell reactivity.

9.3 Study Design

This is a two-arm randomized study. At the time of study entry, eligible subjects will be randomized to either Group A or Group B.

Group A: Subjects will have surgery prior to starting course 1 of IC treatment.

Group B: Subjects will have surgery after course 1 and before course 2 of IC treatment.

The rationale for the study design is described in detail in Section 1.3.4.

9.3.1 Randomization/Stratification

The randomization will be based on a permuted block of size 4, stratified by type of surgical resection (“extensive” vs. “non-extensive”). “Extensive” surgical resection is defined as: Resection requires thoracotomy, laparotomy or excision of deep soft tissue metastases in 3 or more anatomic locations. “Non-extensive” surgical resection is defined as: Resection requires cutaneous/subcutaneous excision and/or excision of deep soft tissue disease in only 1 or 2 locations.

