1.5.4.4 Surgical resection randomization –Before versus After Course 1 therapy

All subjects will be followed for time to recurrence and overall survival measured from the completion of their second course of treatment. Subjects in all study groups will have spent equivalent time since study entry in getting to this point: all will have had their surgical resection and their first 2 courses of study treatment. The differences will be in the timing of their resection (pretreatment in Group B and after Course 1 in Group A). While Group A subjects also will be providing informative data regarding the influence of one course of hu14.18-IL2 on the histopathology of the resected tumor, Group B will be providing essential histopathology control data. Furthermore, any future use of this approach for patients that can achieve MRD surgically (i.e., a Phase III trial that might be based on data from this study), would be anticipated to utilize the treatment schedule for Group B, as it would allow administration of the optimal therapy (whichever this pilot trial suggests that to be) to patients that can achieve a CR prior to receiving all courses of therapy. Thus obtaining clinical and lab data from all study groups is important. Even though the numbers are small, and there will be much variability in assays and subject characteristics, it makes sense for these treatment groups to be treated at the same time (rather than sequentially), and with an effort made to keep both groups comparable in characteristics and assessments. Thus, subjects entered into this study, following confirmation of meeting all eligibility criteria and obtaining signed informed consent, will be randomized to either of the treatment groups. The randomization will stratify subjects for the single variable of “extent of surgery required”. Namely, subjects needing a thoracotomy, a laparotomy, or deep soft tissue excisions in 3 anatomic locations would be considered to need “extensive resection”, while those subjects requiring only superficial cutaneous excisions or deep soft tissue excision in only 1 or 2 locations would be considered to need “non-extensive resection”. Randomization will be performed for all subjects entered into the study, in order to keep all treatment groups comparable to each other with respect to the number of subjects requiring extensive versus non-extensive resection.

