1.5.4.6 Number of subjects to be entered

The number of subjects to be entered into this study is based on our desire to obtain pilot clinical experience with these regimens in melanoma subjects with MRD and our desire to have adequate tumor tissue from both groups to be able to make laboratory comparisons between them. This has lead us to study groups with 8 subjects each, for a total of 16 subjects. The statistical basis for these conclusions can be found in Section 9.0.

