4.2 Subjects will be registered directly into Oncore by the Melanoma Research Staff

4.3 Subjects must meet all of the eligibility requirements listed in Section 3.0.

4.4 The following information will be requested during registration:

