4.4.1 Protocol number

4.4.2 Investigator's name

4.4.3 Subject's name and medical record number

4.4.4 Subject demographics

4.4.5 Gender

4.4.6 Birthday (MM/DD/YYYY)

4.4.7 Race (according to the NCI classification)

4.4.8 Will complete surgical resection be “extensive” (i.e., require thoracotomy, laparotomy or excision of deep soft tissue metastases in 3 anatomic locations) or “non-extensive” (i.e., not require thoracotomy, laparotomy or excision of deep soft tissue metastases in 3 anatomic locations, but require only cutaneous/subcutaneous excisions and/or excision of deep soft tissue disease in only 1 or 2 locations)?

4.5 Subjects then will be randomized to one of the two study groups. (See Section 9.3.1 for more details on randomization process.)

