8.1.2.3 Packaging and labeling of hu14.18-IL2

Hu14.18-IL2 will be provided to the trial site in open-label, supplies for admixture and administration at the site. No drug will be dispensed directly to subjects. Hu14.18-IL2 was manufactured according to current Good Manufacturing Practices (cGMP).

The information on the vial label will be in accordance with all applicable regulatory requirements. The vial label will include the drug name and concentration, volume of drug contained in the vial, lot number, and storage conditions, as well as a notice that federal law restricts the use of the product to investigational use.

The Investigator/Designee is advised to place a similar label on the infusion bag after admixture. In accordance with applicable regulatory requirements, it is recommended that the infusion bag label identify the investigational drug, lot number, the date and time of admixture, the admixture expiration date and time (i.e., maximum of 12 hours after admixture = 4 hours of infusion plus 8 hours of storage), amount of drug added, infusion rate, and storage conditions prior to administration. The infusion bag label should include the UW protocol study number (CO05601), the subject's initials, and the subject's study identification number.

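### The single disclosed block size of 4, in an open-label one-centre trial with no stated list holder, lets anyone tracking allocations by stratum deduce about 25-33% of assignments

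*Combined protocol and SAP*

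**What the plan says.** Section 9.3.1 gives the whole allocation rule: "The randomization will be based on a permuted block of size 4, stratified by type of surgical resection". The two strata are extensive and non-extensive resection. Section 1.5.4.4 confirms that this is the only stratification factor and places randomisation after eligibility is confirmed and consent is signed.

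On who does what, item 4.2 says: "Subjects will be registered directly into Oncore by the Melanoma Research Staff". Item 4.4.8 collects the surgery stratum at registration. Item 4.5 continues, "Subjects then will be randomized to one of the two study groups", and points to Section 9.3.1 for detail. Neither section names a list holder, a central allocation step or any means of concealing the next assignment.

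The arms are surgery before or after Course 1, so each allocation is visible once made. Section 8.1.2.3 adds: "Hu14.18-IL2 will be provided to the trial site in open-label, supplies for admixture and administration at the site". Accrual is planned from one centre's experience (Section 9.3.2), and "we will accrue up to 20 eligible subjects (10 per arm) in total", to yield 8 evaluable subjects per arm.

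The A and B labels in Section 9 are the reverse of those in the Schema and Section 5. The arms are therefore named here by the timing of surgery.

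**The concern.** With one known block size and visible past allocations, the block structure gives away some future assignments. The fourth place in a block is always known, and the third is known whenever the first two match.

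This bears on the first primary objective. Section 1.5.4.3 explains that pre-study biopsies are small and handled differently, so tumours resected before any treatment are needed as the control. Randomisation is what makes them a fair control.

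Entry also involves judgement. The surgical oncologist decides resectability (Section 5.2.3), and the stratum depends on the operation expected. The elective biopsy substudy exists only in the arm treated before surgery and needs accessible lesions (Sections 7.3.2 and 7.8), which gives staff an innocent reason to prefer that arm for some subjects. A positive reading is anything above none (Section 9.3.2), so necrosis or infiltrate present at baseline counts directly. Blinded slide reading cannot undo selection at entry.

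**Working it through.** **Plan's own figure.** The plan gives no predictability figure. The nearest stated figure is power for the histology test: 8 per arm, two-sided 0.10, at least 82% for a 70-point difference and at least 64% for a 60-point difference. A continuity-corrected calculation at the least favourable rates gives 82.1% (0.15 v 0.85) and 62.5% (0.20 v 0.80). Exact Fisher enumeration gives 80.0% and 61.4% at those rates. The stated figures are reproduced to within about 3 points, so the test below is the planned one.

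**Inputs.** Two arms at 1:1, blocks of 4 and two strata (Sections 9.3.1 and 9.3.2); 16 evaluable or up to 20 accrued. The split between strata is not given, so all splits are covered.

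**One block.** There are six equally likely sequences with two subjects per arm.
- Chance that the assignment is certain at positions 1 to 4: 0, 0, 1/3, 1. Sum 4/3, and (4/3)/4 = 33.3%.
- Chance that guessing the under-filled arm is right: 1/2, 2/3, 2/3, 1. Sum 17/6, and (17/6)/4 = 17/24 = 70.8%.

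**Two strata with incomplete last blocks.** An unfinished block with two places filled adds no certain assignment.

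| Total | Split | Certain | Share | Guess right |
|---|---|---|---|---|
| 16 | 8/8 | 4 × 4/3 = 5.3 | 33% | 71% |
| 16 | 6/10 | 3 × 4/3 = 4.0 | 25% | 68% |
| 20 | 8/12 | 5 × 4/3 = 6.7 | 33% | 71% |
| 20 | 10/10 | 4 × 4/3 = 5.3 | 27% | 68% |

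All other splits lie between these values.

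**Illustration 1: steering only when certain (assumed, no true effect, complete blocks).** Take a base positive rate of 50%. In the certain third of places, subjects are chosen so that the chance of a positive reading shifts by *d*, up for one arm and down for the other. The false difference is 2 × *d* × 1/3.

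| *d* (points) | False difference (points) | Fisher rejection rate |
|---|---|---|
| 0 | 0 | 2.5% |
| 10 | 7 | 3.1% |
| 20 | 13 | 4.5% |
| 30 | 20 | 6.8% |
| 40 | 27 | 10.6% |

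**Illustration 2: steering every subject on the best guess (assumed).** With guess rate *k*, the false difference is (2*k* − 1) × (high rate − low rate).
- *k* = 17/24, 60% v 20%: (10/24) × 40 = 16.7 points; rejection rises from 2.7% to 6.2%.
- *k* = 17/24, 80% v 20%: (10/24) × 60 = 25 points; rejection 10.5%.
- *k* = 41/60 (20 subjects split 10/10), 60% v 20%: (22/60) × 40 = 14.7 points; rejection about 5%.

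**Effect of varying the block size.** Simulation with an observer who knows the possible sizes but not the current one, in two equal strata:

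| Sizes | Certain, 16 / 20 subjects | Guess right, 16 / 20 subjects |
|---|---|---|
| 4 only | 33% / 27% | 71% / 68% |
| 4 and 6 | 6% / 6% | 67% / 68% |
| 4, 6 and 8 | 3% / 2% | 66% / 66% |

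Certainty falls sharply but the best guess hardly moves. At 20 subjects split 10/10, the 60% v 20% bias goes from 14.7 points to (2 × 0.679 − 1) × 40 = 14.3.

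**The case against.** The strongest reply is that steering would be hard in practice.
- Section 9.3.2 expects 20 subjects in 24 months, under one a month across two strata, so there is rarely a pool to choose from.
- Section 7.1 requires scans within 3 weeks of registration and laboratory tests within 2 weeks of randomisation, which limits holding a subject back.
- Section 7.5.1 says prior material will mostly be too small for extensive study of the infiltrate, so staff could seldom foresee a positive reading.
- The stratum definition is largely objective, and eligibility and consent already precede randomisation.
- The plan also has a blinded second reader, a paired comparison within the arm treated before surgery, and a baseline comparison. Sections 7.5.4 and 9.2.1 disagree on whether the first reader is blinded too.

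All of this stands and lowers the likely harm. None of it stops the assignments from being deducible, and neither blinded reading nor 8 subjects per arm would reveal or correct selection at entry.

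A reader might infer more than the text supports:
- That the list is open to staff. Concealment is undescribed, not shown to be absent.
- That the block size is public. It is in the protocol staff work from, but Section 8.1.3 treats such documents as confidential.
- That the research staff also decide the stratum. The plan says only that they register subjects.

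**Conclusion.** The point holds as a weakness in the allocation procedure. About 25-33% of assignments are deducible with certainty, and 68-71% of best guesses would be right, for someone who tracks past allocations within each stratum. A reader might take one third as the general figure; it is exact only for complete blocks.

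Nothing in the documents shows that anyone predicted or steered an assignment. Nor do they support a claim that the histology test loses control of its error rate. With 8 per arm its true size is about 2.5% at a 50% positive rate, and in the illustrations it passes 10% only under strong steering. Those steering rates are assumptions with no source in the plan. The main risk is a biased estimate of the histological difference, in a pilot meant to judge whether further evaluation is warranted.

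The figures exclude any added predictability from refilling positions in a group (Section 5.3.1.3). This is a change to consider.

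**What to change.** In Section 9.3.1, replace the fixed block of 4 with permuted blocks of randomly varying size, still stratified by type of surgical resection. Keep the sizes (for example 4 and 6) in a document held by the biostatistics office and out of the clinical protocol. State that the statistician generates and holds the list for subjects not yet randomised. State also that each assignment is released only after eligibility, consent and stratum have been entered and locked. Whether Oncore can do this should be confirmed, since the plan describes it only for registration.

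All parts are needed, because varying the size alone barely changes the best-guess rate for someone who knows the sizes.

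The cost is a short protocol edit and a new list. Sample size, visits and analysis stay as they are. Final balance changes little. Over stratum splits of 10/10, 14/6, 16/4, 8/8 and 12/4, mixed 4/6 blocks give a mean absolute arm difference of about 0.7-1.0 subjects, against 0-1.1 with fixed blocks of 4. A difference of 4 or more occurs in about 2-4% of trials, against 0-6%.
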